15.6. Appendix 6: Genetic Research

Genetic Research Objectives and Analyses

The objectives of the genetic research are to investigate the relationship between genetic variants and:

- Response to medicine, including {GSK2816126} or any concomitant medicines;
- {Disease susceptibility, severity, and progression and related conditions}

Genetic data may be generated while the clinical study is underway or following completion of the study. Genetic evaluations may include focused candidate gene approaches and/or examination of a large number of genetic variants throughout the genome (whole genome analyses). Genetic analyses will utilize data collected in the clinical study and will be limited to understanding the objectives highlighted above. Analyses may be performed using data from multiple clinical studies to investigate these research objectives.

Appropriate descriptive and/or statistical analysis methods will be used. A detailed description of any planned analyses will be documented in a Reporting and Analysis Plan (RAP) prior to initiation of the analysis. Planned analyses and results of genetic investigations will be reported either as part of the clinical RAP and study report, or in a separate genetics RAP and report, as appropriate.

Study Population

Any subject who is enrolled in the clinical study, can participate in genetic research. Any subject who has received an allogeneic bone marrow transplant must be excluded from the genetic research.

Study Assessments and Procedures

A key component of successful genetic research is the collection of samples during clinical studies. Collection of samples, even when no *a priori* hypothesis has been identified, may enable future genetic analyses to be conducted to help understand variability in disease and medicine response.

- A 6 ml blood sample will be taken for Deoxyribonucleic acid (DNA) extraction. Blood sample is collected at the baseline visit, after the subject has been randomized and provided informed consent for genetic research. If a subject initially declines to participate in genetic research and then changes their mind, a sample should be obtained at the earliest opportunity. Instructions for collection and shipping of the genetic sample are described in the laboratory manual. The DNA from the blood sample may undergo quality control analyses to confirm the integrity of the sample. If there are concerns regarding the quality of the sample, then the sample may be destroyed. The blood sample is taken on a single occasion unless a duplicate sample is required due to inability to utilize the original sample.

The genetic sample is labelled (or “coded”) with the same study specific number as used to label other samples and data in the study. This number can be traced or linked back to the subject by the investigator or site staff. Coded samples do not carry personal identifiers (such as name or social security number).

Samples will be stored securely and may be kept for up to 15 years after the last subject completes the study or GSK may destroy the samples sooner. GSK or those working with GSK (for example, other researchers) will only use samples collected from the study for the purpose stated in this protocol and in the informed consent form. Samples may be used as part of the development of a companion diagnostic to support the GSK medicinal product.

Subjects can request their sample to be destroyed at any time.

Informed Consent

Subjects who do not wish to participate in the genetic research may still participate in the clinical study. Genetic informed consent must be obtained prior to any blood being taken for genetic analysis.

Subject Withdrawal from Study

If a subject who has consented to participate in genetic research withdraws from the clinical study for any reason other than being lost to follow-up, the subject will be given a choice of one of the following options concerning the genetic sample, if already collected:

- Continue to participate in the genetic research in which case the genetic DNA sample is retained

- Discontinue participation in the genetic research and destroy the genetic DNA sample

If a subject withdraws consent for genetic research or requests sample destruction for any reason, the investigator must complete the appropriate documentation to request sample destruction within the timeframe specified by GSK and maintain the documentation in the site study records.

Genotype data may be generated during the clinical study or after completion of the clinical study and may be analyzed during the clinical study or stored for future analysis.

- If a subject withdraws consent for genetic research and genotype data has not been analyzed, it will not be analyzed or used for future research.
- Genetic data that has been analyzed at the time of withdrawn consent will continue to be stored and used, as appropriate.

Screen and Baseline Failures

If a sample for genetic research has been collected and it is determined that the subject does not meet the entry criteria for participation in the clinical study, then the investigator should instruct the participant that their genetic sample will be destroyed. No forms are required to complete this process as it will be completed as part of the consent and sample reconciliation process. In this instance a sample destruction form will not be available to include in the site files.

Provision of Study Results and Confidentiality of Subject's Data

GSK may summarize the genetic research results in the clinical study report, or separately and may publish the results in scientific journals.

GSK may share genetic research data 'with other scientists to further scientific understanding in alignment with the informed consent. GSK does not inform the subject, family members, insurers, or employers of individual genotyping results that are not known to be relevant to the subject's medical care at the time of the study, unless required by law. This is due to the fact that the information generated from genetic studies is generally preliminary in nature, and therefore the significance and scientific validity of the results are undetermined. Further, data generated in a research laboratory may not meet regulatory requirements for inclusion in clinical care.

Section 15.6 Appendix 6: Response Criteria for Multiple Myeloma

Consensus Recommendations [Rajkumar, 2011] for the Uniform Reporting of Clinical Trials: Report of the International Myeloma Working Group (IMWG) Consensus Panel

Response Criteria [Durie, 2006]

sCR (stringent complete response):

Complete response as defined below plus:

- normal free light chain (FLC) ratio and
- absence of clonal cells in bone marrow by immunohistochemistry or 2-4 color flow cytometry.

CR (complete response):

- Negative serum and urine immunofixation, and
- Disappearance of any soft tissue plasmacytomas, and
- $\leq 5\%$ plasma cells in bone marrow.

VGPR (very good partial response):

- Serum and urine M-component detectable by immunofixation but not on electrophoresis OR
- 90% or greater reduction in serum M-component plus urine M-component $< 100\text{mg}/24\text{h}$.

PR (partial response):

- $\geq 50\%$ reduction of serum M-protein and reduction in 24 hour urinary M-protein by $\geq 90\%$ or to $< 200\text{mg}/24\text{h}$, and
- If the serum and urine M-protein are not measurable, a $\geq 50\%$ decrease in the difference between involved and uninvolved free light chain levels is required in place of the M-protein criteria. If serum and urine M-protein are not measurable, and serum free light chain assay is also not measurable, $\geq 50\%$ reduction in bone marrow plasma cells is required in place of M-protein, provided baseline bone marrow plasma cell percentage was $\geq 30\%$, and
- In addition to the above listed criteria, if present at baseline, a $\geq 50\%$ reduction in the size of the soft tissue plasmacytomas is also required.

MR (minimal response):

- $\geq 25\%$ but $\leq 49\%$ reduction of serum M-protein and reduction in 24 hour urinary M-protein by 50% to 89%, AND
- If present at baseline, 25% to 49% reduction in the size of soft tissue plasmacytomas is also required.
- No increase in size or number of lytic bone lesions (development of compression fracture does not exclude response).

SD (stable disease):

- Not meeting criteria for CR, VGPR, PR, MR or Progressive Disease.

Progressive Disease:

Requires any one or more of the following:

- Increase of $\geq 25\%$ from lowest response value in any one or more of the following:
 - serum M-component (absolute increase must be ≥ 0.5 g/dl), or
 - urine M-component (absolute increase must be ≥ 200 mg/24h), or
 - the difference between involved and unininvolved free light chain levels (absolute increase must be > 10 mg/dl): only for subjects without measurable serum and urine M-protein levels, or
 - bone marrow plasma cell percentage (the absolute % must be $\geq 10\%$) – only for subjects without measurable serum and urine M-protein levels and without measurable disease by FLC level.
 - definite development of new bone lesions or soft tissue plasmacytomas or definite increase in the size of existing bone lesions or soft tissue plasmacytomas.
 - development of hypercalcemia (corrected calcium > 11.5 mg/dl or 2.65 mmol/l) that can be attributed solely to the plasma cell proliferative disorder.
- a. All response categories (CR, sCR, VGPR, PR, MR and Progressive Disease) require two consecutive assessments made at any time before the institution of any new therapy; CR, sCR, VGPR, PR, MR, and SD categories also require no known evidence of progressive or new bone lesions if radiographic studies were performed. VGPR and CR categories require serum and urine studies regardless of whether disease at baseline was measurable on serum, urine, both, or neither. Radiographic studies are not required to satisfy these response requirements. Bone marrow assessments need not be confirmed. For Progressive Disease, serum M-component increases of more than or equal to 1 g/dL are sufficient to define relapse if starting M-component is ≥ 5 g/dL.
- b. Clarifications to IMWG criteria for coding CR and VGPR in subjects in whom the only measurable disease is by serum FLC levels: CR in such subjects indicates a

normal FLC ratio of 0.26 to 1.65 in addition to CR criteria listed above. VGPR in such subjects requires a > 90% decrease in the difference between involved and uninvolved FLC levels.

- c. Clarifications to IMWG criteria for coding Progressive Disease: Bone marrow criteria for Progressive Disease are to be used only in subjects without measurable disease by M protein and by FLC levels; “25% increase” refers to M protein, FLC, and bone marrow results, and does not refer to bone lesions, soft tissue plasmacytomas, or hypercalcemia and the “lowest response value” does not need to be a confirmed value.

AMENDMENT [4]

Where the amendment applies

This amendment applies to all investigator sites participating in this study

Summary of Amendment Changes with Rationale

Based on emerging data and guidance from ANSM following the submission of our CTA, GSK agreed to update the protocol for the following:

- Update the instructions for investigational product to restrict the storage duration of the final diluted solution to not more than 12 hours at ambient temperature (Protocol previously noted storage up to 48 hours),
- Instruct the investigators to inform their patients that they should: minimize or avoid prolonged exposure to natural or artificial sunlight; to wear sunglasses and loose fitting clothing to protect the skin; and to use a broad spectrum sunscreen on any uncovered areas of the body if outdoors.
- Amend the protocol to extend the period of post treatment contraception for women to 2 weeks (14 days).

In addition, updates to the timing and frequency of pregnancy testing were updated to align with current GSK SOP. Text was added to protocol to clarify those females who become pregnant while on study should be immediately withdrawn from study treatment and withdrawn from the study.

Lastly, the administration of ondansetron and palonosetron was clarified to allow oral doses up to 8mg TID and exclude IV.

AUTHORS:

PPD

Sponsor/medical monitor Information Page

Medical Monitor and Sponsor Contact Information:

Role	Name	Day Time Phone Number	After-hours Phone/Ce ll/ Pager Number	Fax Number	GSK Address
Primary Medical Monitor	[name]	PPD			[name], [name] [name], USA PPD
Secondary Primary Medical Monitor	PPD [name]	PPD			[name] PPD
Secondary Medical Monitor	PPD MD	Office: PPD Cell: PPD	PPD		[name], [name] [name], USA PPD

PROTOCOL SYNOPSIS

REVISED TEXT

INCLUSION/EXCLUSION CRITERIA:

Part 1: Inclusion Criteria

8. Women of childbearing potential must have a negative serum pregnancy test within 47 days of first dose of study treatment and agree to use effective contraception, as defined in Section 10.1, during the study and for at least one two weeks (14 days) following the last dose of study treatment.

Section 4. INVESTIGATIONAL PRODUCT

REVISED TEXT

4.1: Description of Investigational Product

Table 5 Investigational Product

Product name:	GSK2816126 Injection, 15 mg/mL, 30 mL vial with 25 mL fill volume
Formulation description:	Solution containing 15 mg/mL GSK2816126 in water for Injection, methanesulfonic acid, Captisol and acetic acid
Dosage form:	A solution stored at 2-8°C, protected from light
Unit dose strength(s)	15 mg/mL
Route/Regimen	Delivered as an intravenous solution over 2 - 4 hours Study drug can be diluted into saline or dextrose for a final volume of 250ml at ambient temperature and normal room lighting up to 48 12 hours prior to infusion. PVH, PE and PA bags and tubing are all acceptable
Physical description:	A clear, pale yellow coloured solution, essentially free from visible particles of foreign matter

Section 5 STUDY POPULATION

REVISED TEXT

Section 5.2 Subject Selection Criteria

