Urine for Metabolite (Part 2 PK/PD expansion cohort only)	On Day 15, urine samples should be collected while subject is in the office		Day 1 prior to first dose and from 0 to 24h		Day 15 from 0 to 8 h			
Bile for metabolite (Part 2 PK/PD expansion cohort only) – at least 4 subjects)					Day 15			
Plasma for 4β-hydroxycholesterol and cholesterol assay (Part 2 PK/PD expansion cohort only)			X (Day 1 prior to First Dose)			X		

STUDY PHASE	VISIT	SCREEN	First Treatment Period Cycle 1				Continuation Phase Cycle 2 and beyond	Follow- Up ^j	
			Day 1 and 4 ^a	Day 8 and 11 ^a	Day 15 and 18 ^a	Day 21			
			VISIT WINDOW (\pm days)	-14					
Disease Assessments for Lymphoma Subjects: Baseline disease assessments at screening and repeated 8 weeks after dosing is initiated and every 12 weeks thereafter									
CT ^k	Must be completed within 4 weeks of first dose of GSK2816126 and repeated 8 weeks after dosing is initiated. Every 12 weeks thereafter	X					X	X ^d	
Positron emission tomography (PET)	The use of standalone PET or PET in combination with CT scan is optional. Standalone PET does not replace CT	X ^e					X ^e	X ^{d,e}	
Bone Marrow biopsy)	See Section 7.7	X					X ^f	X ^f	
B symptoms	See Section 7.7	X	X	X	X	X	X		
Disease Assessments for Multiple Myeloma (MM) subjects: Baseline disease assessments at screening, week 4 and then every 6 weeks thereafter unless otherwise noted									
Disease Characteristics	Every 6 weeks after Wk4, Including cytogenetics as appropriate	X					X		
Total Protein, CRP, β 2 microglobulin	Every 6 weeks after Wk4	X					X		
Response Assessment	Every 6 weeks after Wk4; Response criteria in Appendix 6						X		

STUDY PHASE	VISIT	SCREEN	First Treatment Period Cycle 1				Continuation Phase Cycle 2 and beyond	Follow- Up ^j	
			Day 1 and 4 ^a	Day 8 and 11 ^a	Day 15 and 18 ^a	Day 21			
			VISIT WINDOW (\pm days)	-14					
SPEP, FLC assay, quantitative immunoglobulins (IgG, IgA, IgM)	Not required for subjects with non-secretory MM	X					X		
UPEP	Only required if paraprotein is present in urine	X							
Extramedullary Disease Assessment	Only required for MM with extramedullary disease	X							
BM aspirate and biopsy	Required for non-secretory MM, or as appropriate for other subjects	X				Day 18	Week 10, Day 1		
Disease Assessments for Solid Tumors: Baseline disease assessments at screening and repeated every 8 weeks after dosing is initiated									

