All subjects who discontinue from study treatment will have safety/disease assessments at the post study treatment Follow Up Visit as specified in the Time and Events Tables.

Section 7.2 Demographic/Medical History and Baseline Assessments

Rationale for Change: Clarified baseline assessments required based on tumor type.

REVISED TEXT

- Disease characteristics for all subjects including:
 - Date of initial diagnosis
 - Initial diagnosis tumor histology
 - ECOG performance status at initial diagnosis
 - ~~LDH level at initial diagnosis~~
 - Tumor location involvement at initial diagnosis
 - Previous cancer treatments (e.g., cytotoxics, radiotherapy, maintenance, surgery)
 - Ongoing toxicities related to previous treatment

- Best response to previous treatment(s)
- Date of relapse/refractory diagnosis
- Tumor histology (if relapse/refractory tumor biopsy completed). For Part 2 subjects, tumor biopsy is mandatory for inclusion. See Section 7.6.5.
- ~~Ann Arbor stage of relapse/refractory diagnosis for NHL~~
- ECOG performance score at time of first relapse/refractory diagnosis (as applicable)
- ~~LDH level at time of first relapse/refractory diagnosis (as applicable)~~
- Diagnostic quality CT imaging with contrast within 28 days of first dose of study treatment identifying nodes, nodal masses, spleen/liver nodules and, if applicable measurable extra nodal disease. Diagnostic quality CT imaging is the preferred method of disease assessment. If PET/CT has been performed within this window, diagnostic CT will not be required. See Section 7.7 for further information.
- If completed and will be utilized for assessment of disease, PET imaging within 28 days of first dose of study treatment. Images may be obtained from standalone PET scanners or via combination PET/CT scanners. Standalone PET does not replace diagnostic CT. See Section 15.4 for further information.
- For NHL, unilateral or bilateral bone marrow biopsy within 35 days prior to commencing study therapy.
- Clinical laboratory tests: hematology, clinical chemistry, coagulation parameters
- Serum beta-human chorionic gonadotropin (β -HCG) pregnancy test for female subjects of childbearing potential only
- 12-lead ECG
- ECHO or MUGA
- Review of concomitant medications
- Baseline assessments for subjects with GCB-DLBCL
 - Ann Arbor stage of initial diagnosis for NHL
 - Ann Arbor stage of relapse/refractory diagnosis for NHL
 - GCB testing confirming status
 - LDH level at initial diagnosis

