Disease assessment may include imaging and physical examination (as indicated for palpable/superficial lesions). Refer to Appendix 4 for more details on response assessment criteria.

- Disease assessment for lymphomas will be completed within 4 weeks of first dose of GSK2816126 and repeated 8 weeks after dosing is initiated, every 12 weeks thereafter, and at the final study visit.
- Disease assessment for solid tumors will be completed withinat 48 weeks of first dose of GSK2816126 and repeated every 8 weeks after dosing is initiatedthereafter, and at the final study visit.
- Disease assessment for MM will be completed within 4 weeks of first dose of GSK2816126, week 4 and repeated every 6weeks thereafter.

Section 7.7 Evaluation of Anti-Cancer Activity

REVISED TEXT

For subjects with NHL, the following B symptoms should be assessed at the time points in the Time and Events Table (Section 7.1):

- night sweats without signs of infection
- unintentional weight loss of $\geq 10\%$ within the previous 6 months
- recurrent, unexplained fever of greater than 38°C for 2 weeks without signs of infection

If a lymphoma subject had involvement of bone marrow at baseline, and a CR is suspected, a bone marrow biopsy must be obtained ~~as described in Section 7.2.1~~. A repeat bone marrow biopsy will be performed within 8 weeks of the imaging confirmed CR in accordance with the response guidelines (See Appendix 4: Section 15.4 for additional details).

Tumor response will be assessed as outlined above and in the Time and Events Schedule by the investigator using:

- Lymphoma Subjects: Revised Response Criteria for Malignant Lymphoma (RRCLM)(Appendix 4)
- Solid Tumor RECIST 1.1 (Appendix 5)

- Multiple Myeloma: International Myeloma Working Group (IMWG) (Appendix 6)
- Prostate: RECIST 1.1 and PSA (Appendix 7)

Section 7.8 Genetic Research

REVISED TEXT

The information regarding genetic research is included in Appendix 8 Appendix 6.

Section 8.3.1 Liver Chemistry Stopping Criteria

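### Myeloma responses and progressions need two consecutive assessments, but none is scheduled after treatment stops, so a first value at the last on-treatment assessment is confirmed only by an unscheduled repeat

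*Protocol*

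**What the plan says.** Four places in the protocol bear on this.

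- **Appendix 6, Response Criteria for Multiple Myeloma, note a.** "All response categories (CR, sCR, VGPR, PR, MR and Progressive Disease) require two consecutive assessments made at any time". The sentence sets no minimum gap; the only limit is that the assessments are "two consecutive assessments made at any time before the institution of any new therapy". One exception follows: "Bone marrow assessments need not be confirmed".
- **Section 7.1, Table 6, myeloma block.** The block heading reads "Baseline disease assessments at screening, week 4 and then every 6 weeks thereafter unless otherwise noted", and the Response Assessment row reads "Every 6 weeks after Wk4; Response criteria in Appendix 6". No myeloma row has an entry under Follow-Up. The lymphoma CT, solid-tumour CT/MRI and PSA rows do. Footnote j puts the Follow-Up visit 30 days after the last dose.
- **Section 7.7.** "Disease assessment for MM will be completed within 4 weeks of first dose of GSK2816126, week 4 and repeated every 6weeks thereafter". The lymphoma and solid-tumour lines add an assessment at the final study visit; the MM line does not.
- **Section 6.3.** "All subjects who discontinue from study treatment will have safety/disease assessments at the post study treatment Follow Up Visit as specified in the Time and". The sentence closes by naming the schedule tables, which for these assessments means Table 6.

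The Part 2 primary endpoint is the proportion of subjects with CR or PR under the response criteria (Section 2.2), so note a decides who counts as a responder against the Table 18 boundaries.

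**The concern.** A confirmation rule works only if the schedule supplies the second assessment. On treatment it does. For a myeloma subject whose treatment stops after a first qualifying value, it does not: the visit that follows carries no myeloma response assessment and no M-protein or free light chain test.

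Two results are exposed. In the primary endpoint, a subject with a real but once-measured response may be counted as a non-responder, which pulls the observed rate down in a cohort of at most 40. In progression-free survival, a rising value that coincides with the end of treatment may stay unconfirmed. An analysis plan can say how to score such cases, but it cannot recover samples that were never scheduled.

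**Working it through.** **1. The schedule against the rule.** Scheduled myeloma assessments fall at weeks 4, 10, 16, 22 and so on (4 + 6i). Six weeks, or 42 days, is the visit spacing, not a confirmation interval, since note a sets none. If the last dose is given close to an assessment with a first PR or PD value, the next scheduled assessment would have been 42 days later. The Follow-Up visit, at 30 days, falls inside that gap and could supply the second value, but Table 6 orders no myeloma assessment there. Section 6.3 adds nothing, because it points back to Table 6.

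**2. Possible backstop.** Section 7.7 also asks for a disease assessment at withdrawal if the last radiographic assessment is more than 8 weeks old and progression is not documented. Note a says radiographic studies are not needed for myeloma response, so this trigger does not reliably reach subjects followed on serum and urine.

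**3. The plan's own figures.** Inputs from Section 12.2.2 and Table 18: looks after every subject from n = 14 to 40; null rate 10%, alternative 25%; stop for futility at or below b(n), where b(n) is 1 for n = 14–20, 2 for 21–26, 3 for 27–31, 4 for 32–36, 5 for 37–39 and 6 at 40. Success is therefore 7 or more responders of 40.

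Let f(n,k) be the probability of still being in the trial with k responders among n. Then f(n,k) = (1 − p)·f(n−1,k) + p·f(n−1,k−1), set to zero for k ≤ b(n) once n ≥ 14. The probability of success is the sum of f(40,k) over k ≥ 7.

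| | Stated | Recomputed |
|---|---|---|
| Type I error, p = 0.10 | 0.072 | 0.0721 |
| Power, p = 0.25 | 0.814 | 0.8142 |
| Expected N and early termination, p = 0.10 | 20.82; 89.0% | 20.82; 89.0% |
| Expected N and early termination, p = 0.25 | 36.56; 16.7% | 36.56; 16.7% |

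The stated design reproduces.

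**4. Illustration of loss.** Let m be the share of true responders who stop treatment after the first qualifying value and also have no repeat before new therapy. The scored rate is 0.25·(1 − m). The documents give no value for m, so a range is shown.

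| m (assumed) | Scored rate | Power | Change from 0.814 |
|---|---|---|---|
| 5% | 0.25 × 0.95 = 0.2375 | 0.771 | −0.043 |
| 10% | 0.25 × 0.90 = 0.225 | 0.721 | −0.093 |
| 20% | 0.25 × 0.80 = 0.20 | 0.601 | −0.213 |

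**The case against.** The other side has several good points.

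- **An unscheduled repeat satisfies note a.** Nothing shown forbids a second serum or urine test, including at the Follow-Up visit. A reader might infer that such a response or progression can never be scored, or that the two assessments must be 6 weeks apart. The documents support neither: note a allows any time before new therapy. Marrow findings need no repeat at all. What stands is that confirmation is left to the site's initiative.
- **Follow-Up is not empty for myeloma.** Chemistry is marked there and includes calcium and total protein, and hypercalcaemia is a progression criterion. This does not replace M-protein or light chain measurement.
- **The contrast with other tumours is weaker than the marks suggest.** Under footnote d, Follow-Up scans depend on the time since the previous scan (8 or 12 weeks; the marked-up text runs the old and new figures together), so a subject scanned shortly before stopping might not be rescanned. The final-visit wording in Section 7.7 remains a real difference.
- **One value is not yet progression.** Under note a it need not by itself end treatment. Where treatment does end at that point, the gap remains.
- **The power figures rest on assumptions.** Because the criteria already require confirmation, 25% can be read as a confirmed rate, and discounting it again would double count. That is a fair reading, so the figures are illustrative only.
- **The text may not be final.** The myeloma criteria appear in the change list of an earlier amendment, and the operative appendix is not in the part shown. Amendment 5 lists no change to them, and Section 7.7 still points to Appendix 6. Table 6 is printed twice. The Follow-Up cells of the myeloma rows are empty both times, but one copy also lacks most of their on-treatment marks, so single cells should be checked against the original.

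**Conclusion.** The point holds as a schedule omission. If the protocol is followed as written, no confirmatory myeloma assessment takes place after treatment stops, and a first PR or first PD value at the last on-treatment assessment depends on an unscheduled repeat. The effect on the primary endpoint is towards too few responders.

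Its size cannot be established from the documents. Power of 0.771, 0.721 or 0.601 applies only if 5%, 10% or 20% of responders go unconfirmed and if 25% is the rate before such losses; neither is stated. A reader might also infer that unconfirmed progressions would be censored in progression-free survival. No censoring rule is shown, and efficacy details are deferred to the analysis plan, so that step is not supported.

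**What to change.** - In Table 6, mark Response Assessment and the myeloma serum and urine tests (SPEP, light chains, immunoglobulins and, where applicable, UPEP) under Follow-Up.
- In Section 7.7, give the MM line the same final-study-visit assessment that the lymphoma and solid-tumour lines have.
- Reconcile note a of the myeloma criteria, Table 6, Section 7.7 and Section 6.3, so that the confirmation rule and the schedule agree.

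The cost is blood and urine tests at a visit that already takes place, plus protocol wording; no new visit is needed. No rule on the timing of later therapy is proposed, and the dating and censoring of progression are left to the analysis plan.
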